# Inclusion Criteria Part A Randomization (Day 1):

1. An outpatient prior to Randomization.

*NOTE*: Participant may be screened while an inpatient in an acute care facility/hospital but must be discharged from inpatient medical admission prior to Randomization. Participants residing in an assisted living center, long-term care facility, or rehabilitation ward/center may be randomized.

- 2. Has received a course of SOC CDI antibiotics for the Qualifying CDI episode (for 10 to 21 days, with exact duration, antibiotic type, and dose at the discretion of the Investigator).
- 3. Has an adequate clinical response, defined as  $\leq$  3 unformed stools in 24 hours for 2 or more consecutive days during SOC CDI antibiotics prior to Randomization.
- 4.

   5.

#### Figure 6: Assessment of Inclusion Criteria

Abbreviations: CDI = *Clostridioides difficile* infection; EIA=enzyme immunoassay; PCR=polymerase chain reaction.

[figure not shown]
required

Study

# 4.1 Participant Recruitment and Screening

Written informed consent will be obtained by the Investigator or a qualified person designated by the Investigator from each participant before any trial-specific procedures or assessments are performed. After informed consent has been obtained and within a period of 45 days before IP administration, all Screening procedures will be performed to check eligibility criteria (see Table 4 for more details).

The Investigator will check that all inclusion/exclusion criteria have been documented completely, and the trial Medical Monitor will be required to confirm final eligibility. Once trial eligibility is confirmed, participants will be enrolled. The participant will be assigned a unique participant identification number by the IRT at Screening.

#### 5 PARTICIPANT TREATMENT

#### 5.1 Prior and Concomitant Therapy

#### 5.1.1 SOC Antibiotics for CDI

To be enrolled in the trial, recurrent CDI participants must meet eligibility criteria as they pertain to SOC CDI antibiotics (Section 4).

Acceptable SOC CDI antibiotics include the following (alone or in combination) at the discretion of the Investigator:

- Vancomycin
- Fidaxomicin
- Metronidazole

5.2 Diet

# 5.1.2 Concomitant Therapy and Restricted Medications

# 5.3 Participant Compliance

Investigational product will be administered as a single oral dose under the direct supervision of trial staff on Day 1.

Investigational product accountability must be performed by the trial staff on the day of the visit and recorded on the accountability log, in order to ensure that the participant is compliant with trial requirements. Investigational product accountability is also recorded in the CRF and checked by the Monitor during site visits.

Deviation(s) from the prescribed

dosage regimen should be recorded.

# 6 PART B OPTIONAL OPEN-LABEL TREATMENT FOR RECURRENCE

#### 6.1 Summary

Part B (OLT) is the *optional* OLT arm of the trial and will similarly evaluate the efficacy, safety, and tolerability of CP101, in eligible participants from Part A. Participants in Part A, who experienced an on-trial central laboratory-positive *C. difficile*-related diarrhea within 8 weeks after receiving CP101 or placebo may be eligible.

Participants in Part A who experience a new episode of diarrhea within 8 weeks after Randomization (> 3 unformed stools in 24 hours for 2 consecutive days) will undergo central laboratory stool testing for *C. difficile*. The participant will have an Investigator evaluation (Figure 8) which will include a) review of diarrhea data; b) assessment of stool *C. difficile* testing by central laboratory testing algorithm (Figure 7); and c) the clinical decision to start a course of SOC CDI antibiotics. Participants with multistep central laboratory-positive *C. difficile*-related diarrhea will be eligible for Part B. All participants entering Part B will require confirmation of eligibility by the Medical Monitor.

Under extenuating circumstances and with approval of Medical Monitor, participants who experience *C. difficile*-related diarrhea in Part A may be allowed into Part B, provided there is positive multistep local laboratory *C. difficile*-related diarrhea AND the symptoms are clinically consistent with CDI recurrence.

Participants who meet eligibility criteria will be enrolled into Part B once eligibility has been confirmed. This participant cohort must have received SOC CDI antibiotics (vancomycin, fidaxomicin, and/or metronidazole [Section 4]) over a 10- to 21-day treatment period

All participants in the Part B cohort will be followed from the time of OLT administration of CP101 through their Week 8 trial visit (Day  $57 \pm 3$  days) for the assessment of the primary efficacy endpoint as well as safety follow-up and to Week 24 (Day  $169 \pm 14$  days) for other safety endpoints. Additional trial visits will occur as summarized in the Schedule of Assessments (Table 4). Blood and urine samples for safety laboratory analysis,

will be collected at scheduled trial visits per the Schedule

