### 2.1 Primary Efficacy Objective, Endpoint, and Estimand

Primary Objective	Primary Endpoint
To evaluate the efficacy of a single oral dose of CP101 compared to placebo following SOC CDI antibiotics in preventing CDI recurrence in participants with recurrent CDI	Proportion of participants experiencing a CDI recurrence through Week 8 based on adjudication

The primary clinical question of interest is:

What is the difference in the proportions of participants experiencing CDI recurrence through 8 weeks after randomization to CP101 vs placebo in participants with recurrent CDI regardless of discontinuation of investigational intervention for any reason or change in background medication (dose and product)?

The estimand is described by the following attributes:

• Population:

Adult participants with recurrent CDI who have completed SOC CDI antibiotics for their qualifying episode

• Endpoint:

CDI recurrence through 8 weeks post randomization

• Treatment condition:

CP101 or placebo on Day 1 with 8 week follow-up for recurrence regardless of discontinuation of investigational intervention for any reason, or change in background medication (treatment policy strategy).

• Remaining intercurrent events:

The intercurrent events "intervention discontinuation for any reason" and "change in background medication (dose and product)" are addressed by the treatment condition of interest attribute.

The following intercurrent events will result in an outcome of "recurrence" for the primary efficacy analysis:

- Initiation of rescue medication for CDI (fecal microbiota transplantation [FMT] or full course of SOC antibiotics) prior to 8 weeks post randomization
- Occurrence of *C. difficile*-related diarrhea prior to 8 weeks in a participant who does not qualify for Part B of the study, per central lab testing algorithm, and discontinues the study for any reason
- Participants who enter into Part B of the study however, the *C. difficile*-related diarrhea episode is adjudicated as "no recurrence" by the AB
- Participants who die or experience another debilitating event prior to 8 weeks, which precludes continued participation in the study
- Participants who withdraw consent prior to 8 weeks after randomization
- Participants who are lost to follow-up prior to 8 weeks after randomization

There are no other intercurrent events anticipated at this time.

• Population-level summary:

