### Part B:

Efficacy and Safety Endpoints

- Proportion of participants experiencing CDI recurrence through Week 8 and Week 24;
- Incidence of TEAEs and TESAEs through Week 8 and Week 24.

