### 3.6 Trial Duration

Following a 6-week Screening period, the trial duration will be approximately 24 weeks after the IP administration for participants in Part A who do not experience an on-trial, central laboratory-positive *C. difficile*-related diarrhea through Week 8. This includes an 8-week efficacy and safety assessment and an additional safety and CDI recurrence follow-up through Week 24.

Participants who enter Part B of the trial will be followed through Week 24 following OLT. This includes an 8-week efficacy and safety assessment and an additional safety and CDI recurrence follow-up through Week 24.

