#### of Assessments.

Part B will be independent of the participant's blinded trial group allocation in Part A (i.e., participants entering Part B may have received either CP101 or placebo in Part A). The participant-level blinding of initial trial group allocation will be maintained throughout the course of Part B for the participants, and Investigators. The Schedule of Assessment timelines will restart at Screening for participants who enter trial Part B. Visits are labeled by adding 'OLT-' in front of the visit number in the Schedule of Assessments (Table 4) to distinguish Part B trial visits from Part A trial visits. The secondary efficacy endpoint is the proportion of participants with CDI recurrence through Week 8 and Week 24 of Part B. For the secondary safety endpoint, the incidence rate of TEAEs will be presented by treatment group through Week 8 for Part B. Participants will be followed through 24 weeks for other safety endpoints. On-trial *C. difficile*-related diarrhea will undergo Investigator evaluation as outlined in Section 7.1.2.1. Surveillance for new episodes of diarrhea will be conducted as outlined in in Part A (Section 7.1.2.1) and in the Schedule of Assessments (Table 4).

The Investigator will check that all inclusion/exclusion criteria have been documented completely and the trial Medical Monitor will be required to confirm final eligibility for Part B. Screening for Part B (Section 6.2) may be combined with the relevant scheduled or unscheduled visit during Part A if feasible.

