# 8 STATISTICAL METHODS AND DATA ANALYSIS

# 8.1 Trial Endpoints

Refer to Sections 2.1 and 3.3.

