# 8.3 Analysis Populations

Four analysis populations are planned for the trial:

[figure not shown]
Intent-to-treat population (ITT or All Randomized)	All participants randomized into the trial including those who were not exposed to any IP will be included in the ITT population. Participants in the ITT population will be analyzed according to the treatment group to which they were randomized. Th ITT population will be the primary analysis population for all efficacy analyses.		
The mITT population	All participants in the ITT population who receive at least 1 capsule of IP at Randomization (Day 1).		
Per-protocol population (PP population)	All participants in the mITT population who have received at least 80% of trial medication, completed 8 weeks of follow-up or had adjudicated CDI recurrence prior to the 8-week follow-up and did not have any major protocol deviation that affect the efficacy or safety of the IP.		
Safety population	All enrolled participants who received at least 1 capsule of IP. Unless otherwise stated, the Safety population will be the default analysis population for		

all safety analyses. Analyses of safety will be performed based on treatment received, even if different from the treatment group to which participants were randomized. All safety analyses will be performed on the Safety population.

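### Does Section 6.1's reference to the primary efficacy endpoint in Part B put the primary outcome or the per-protocol population on a second 8-week clock?

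*Protocol*

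**What the plan says.** - Protocol 6.1, first account of Part B follow-up: from open-label CP101 through the Part B Week 8 visit "for the assessment of the primary efficacy endpoint as well as safety follow-up and to Week 24".
- Protocol 6.1, next paragraph: "The secondary efficacy endpoint is the proportion of participants with CDI recurrence through Week 8 and Week 24 of Part B". The same paragraph says that the visit timelines restart on entry to Part B and that Part B visits carry a distinguishing prefix.
- Protocol 2.1: the primary endpoint is "CDI recurrence through 8 weeks post randomization". The events scored as recurrence include entering Part B when the "episode is adjudicated as 'no recurrence' by the AB".
- Protocol 3.3: the primary endpoints stand under Part A. The Part B list gives "Proportion of participants experiencing CDI recurrence through Week 8 and Week 24" without a rank. Section 8.1 adds nothing of its own: "Refer to Sections 2.1 and 3.3".
- Protocol 3.6: "Participants who enter Part B of the trial will be followed through Week 24 following OLT", including a separate 8-week efficacy and safety assessment.
- Protocol 8.3: per-protocol members are mITT participants with at least 80% of trial medication and no relevant major deviation who "completed 8 weeks of follow-up or had adjudicated CDI recurrence prior to the 8-week follow-up". The mITT population is defined by taking at least one capsule at Randomization (Day 1). Section 8.4.1 uses the per-protocol population to repeat the primary endpoint analysis.

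**The concern.** Read literally, 6.1 assigns the primary endpoint of a placebo-controlled comparison to uncontrolled open-label follow-up. That contradicts 2.1 and the next paragraph of 6.1.

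The second worry is membership of the per-protocol population. Section 8.3 names no start for its 8 weeks, and 6.1 restarts the timelines in Part B. A Part B entrant with a Board-confirmed recurrence qualifies through the second limb of the definition, whatever the clock. An entrant whose episode the Board rejected has only the follow-up limb. If that person leaves after 8 weeks from randomization but before open-label Week 8, the choice of clock decides whether a participant scored as a recurrence stays in the per-protocol analysis. A choice left open until unblinding could then be made with the results in view.

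**Working it through.** The protocol gives no figure on this point to reproduce. The check has three steps.

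**1. Can Part B follow-up change a primary outcome?** A Part B entrant's qualifying episode is either confirmed by the Board, which makes it a recurrence, or rejected, in which case 2.1 scores it as a recurrence anyway. The primary outcome is therefore fixed by the time of open-label dosing. Primary outcomes that Part B Week 8 can change: none.

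**2. How far apart are the two clocks?** Let D be the Part A day of diarrhea onset, C the length of the antibiotic course (10 to 21 days in 6.1) and w the wait before open-label dosing. The value of w is not legible in the public text, so I assume 0 or 7 days. Antibiotics are taken to start at onset, which gives earliest dates.

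- Open-label Day 57 on the Part A scale = D + C + w + 56.
- D = 2, C = 10, w = 0: Day 68, with its ±3-day window opening on Day 65.
- D = 57, C = 21, w = 0: Day 134.
- With w = 7, the range is Day 75 to Day 141.

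The Part A Week 8 window is Day 54 to Day 60, so the two windows never overlap. With w = 0 the gap from Day 57 is D + C − 1, or 11 to 77 days.

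Anyone who leaves within that gap has, by construction, passed Day 57 from randomization. In the 77-day case, open-label dosing falls on Day 57 + 21 = Day 78, so the participant completed 8 weeks before Part B treatment began.

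**3. How much could the per-protocol result move?** Let p be the recurrence proportion with the disputed entrants kept, r the share of events that are Board-rejected Part B entrants, and s the share of those who leave in the gap. Dropping the leavers gives

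p′ = p(1 − rs) / (1 − rsp).

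For p I use 25.5% and 38.5%. These are the complements of the PRISM3 figures of 74.5% and 61.5% in Section 1.5.2, read as proportions without recurrence. They are mITT rates from another trial, used only as an illustration. The protocol gives neither r nor s, so both are assumed, and assumed equal in the two arms.

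| r | s | CP101 | Placebo | Difference | Change from 13.0 points |
|---|---|---|---|---|---|
| 0.05 | 0.10 | 25.4% | 38.4% | 12.98 | 0.02 |
| 0.10 | 0.20 | 25.1% | 38.0% | 12.90 | 0.10 |
| 0.20 | 0.30 | 24.3% | 37.0% | 12.70 | 0.30 |

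For the middle row, CP101 is 0.255 × 0.98 / (1 − 0.02 × 0.255) = 0.2499 / 0.9949 = 0.2512. Placebo is 0.385 × 0.98 / (1 − 0.02 × 0.385) = 0.3773 / 0.9923 = 0.3802.

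If every rejected entrant left in the gap (s = 1), the difference would be 12.76, 12.49 or 11.87 points at r = 0.05, 0.10 or 0.20. Those are changes of about 0.2, 0.5 and 1.1 points.

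In head counts, a 216/108 split with every recurrence entering Part B gives 0.255 × 216 + 0.385 × 108 = 55.1 + 41.6 = 96.7 entrants. At r = 0.10 and s = 0.20, about 96.7 × 0.02 = 1.9 people in the whole trial are in dispute.

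**The case for a change.** The strongest case for a change is that the contradiction is plain and the sentence is complete, so no redaction explains it. Section 6.1 cannot be right under 2.1, and correcting a phrase costs almost nothing. On the per-protocol side, 8.3 really does omit a start point, 6.1 restarts the timelines, and 3.6 describes an 8-week assessment separately for each part. An analyst who took those together could reach the open-label clock.

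The first part stands: 6.1 is mislabelled. The sentence closely parallels the Part A follow-up sentence in Section 1.4, with the same visit windows, so a carry-over from that text is a plausible explanation. The missing rank in 3.3 conflicts with nothing, since 6.1 supplies one.

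The second part does not stand as an error.

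- Section 8.3 neither cites 6.1 nor depends on it. Its silence would be the same if 6.1 were worded perfectly.
- The document points to randomization at every relevant place. The treatment condition in 2.1 pairs dosing on Day 1 with 8-week follow-up, 1.4 places Week 8 at Day 57 ± 3, per-protocol is a subset of a population fixed by dosing at Randomization, and it serves to repeat an endpoint counted from randomization.
- The open-label clock requires reading 8.3 as 8 weeks after a second dose, which it does not say.
- Section 8.2 leaves analysis details to a SAP that is finalized before the Week 8 database lock, with the sponsor blinded until then. Only the protocol is at hand, so that detail cannot be counted as missing.

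**Conclusion.** No change to the plan follows. The wording in 6.1 is a clerical slip that 2.1, 3.3 and the next paragraph of 6.1 override. It alters no primary outcome, and the ITT and mITT results, the sample size of about 324 and the interim analysis at about 217 participants are all unaffected. The unnamed start point in 8.3 has one natural reading, from randomization, and every participant in dispute meets it.

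Even on the strained reading, the supportive per-protocol difference moves by about 0.02 to 0.3 points, or by 1.1 points in the extreme case where 20% of events are rejected entrants and all of them leave in the gap. These sizes rest on assumed rejection and leaving rates, taken as equal across arms, and on borrowed PRISM3 rates. The finding that no primary outcome changes rests only on the text of 2.1.

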#### of Assessments.

Part B will be independent of the participant's blinded trial group allocation in Part A (i.e., participants entering Part B may have received either CP101 or placebo in Part A). The participant-level blinding of initial trial group allocation will be maintained throughout the course of Part B for the participants, and Investigators. The Schedule of Assessment timelines will restart at Screening for participants who enter trial Part B. Visits are labeled by adding 'OLT-' in front of the visit number in the Schedule of Assessments (Table 4) to distinguish Part B trial visits from Part A trial visits. The secondary efficacy endpoint is the proportion of participants with CDI recurrence through Week 8 and Week 24 of Part B. For the secondary safety endpoint, the incidence rate of TEAEs will be presented by treatment group through Week 8 for Part B. Participants will be followed through 24 weeks for other safety endpoints. On-trial *C. difficile*-related diarrhea will undergo Investigator evaluation as outlined in Section 7.1.2.1. Surveillance for new episodes of diarrhea will be conducted as outlined in in Part A (Section 7.1.2.1) and in the Schedule of Assessments (Table 4).

The Investigator will check that all inclusion/exclusion criteria have been documented completely and the trial Medical Monitor will be required to confirm final eligibility for Part B. Screening for Part B (Section 6.2) may be combined with the relevant scheduled or unscheduled visit during Part A if feasible.

# 6.2 Part B: Inclusion Criteria (Screening)

The following criteria must be satisfied for entry into Part B of the trial:

#### Inclusion Criteria Part B of the trial:

1. Previously enrolled in Part A: Participants who have an on-trial, central laboratory-positive *C. difficile*-related diarrhea within 8 weeks after receiving CP101 or placebo in Part A defined as:

a) Diarrhea (> 3 unformed stools in 24 hours for 2 or more consecutive days) or diarrhea that does not meet the definition, but the Investigator has a strong clinical suspicion of *C. difficile*-related diarrhea and Medical Monitor has confirmed per study Figure 8;

# AND

b) A stool specimen testing positive for *C. difficile* by central laboratory testing algorithm (or local laboratory-positive under extenuating circumstances such as central lab closure);

# AND

c) Participant has received a course of SOC CDI antibiotics for the most recent CDI event (for 10 to 21 days, with exact duration, antibiotic type, and dose at the discretion of the Investigator);

# AND

d) Participant has had an adequate clinical response, defined as  $\leq 3$  unformed stools in 24 hours for 2 or more consecutive days during SOC CDI antibiotics prior to IP administration.

# **NOTE:** Confirmation of eligibility by Medical Monitor is required before entry into Part B.

# Exclusion Criteria Part B (Screening):

- 1. New onset of any acute, chronic, or unstable medical comorbidity, psychiatric, social, or other circumstances that, in the opinion of the Investigator, may interfere with trial compliance, completion, or accurate assessment of trial outcomes/safety. Examples include but not limited to acute myocardial infarction, acute stroke, uncompensated congestive heart failure, and decompensated liver disease.
- 2. Pregnant, breast-feeding, or planning to become pregnant during the trial.
- 3. Screening nasal PCR test is positive for severe acute respiratory syndrome coronavirus 2 (SARS-CoV-2) and participant exhibits symptoms that in the opinion

of the Investigator, may interfere with trial compliance, completion, or accurate assessment of trial outcomes/safety.

# Inclusion Criteria Part B Open-Label Treatment (Day 1):

The following criteria must be satisfied prior to OLT in Part B of the trial:

1. An outpatient prior to OLT;

**NOTE**: Participant may be screened while an inpatient in an acute care facility but must be discharged from inpatient medical admission prior to IP administration. Participants residing in an assisted living center, long-term care facility, or rehabilitation ward/center are eligible for Part B.

- 2. Has received a course of SOC CDI antibiotics for the on-trial, central laboratory-positive *C. difficile*-related diarrhea (for 10 to 21 days, with exact duration, antibiotic type, and dose at the discretion of the Investigator);
- 3. Has an adequate clinical response, defined as  $\leq$  3 unformed stools in 24 hours for 2 or more consecutive days during SOC CDI antibiotics prior to IP administration;
- 4. 5.
- 7 TRIAL ASSESSMENTS

# 7.1 Assessment of Efficacy

# 7.1.1 Efficacy Parameters

The primary clinical outcome is CDI recurrence confirmed by an independent AB. The primary efficacy endpoint is the proportion of participants with CDI recurrence through Week 8 based on adjudication. Primary, Secondary and Exploratory endpoints are provided in Section 3.3.

